1.2 Secondary Aims

1.2.1 To compare progression-free survival and overall survival between patients receiving dinutuximab, irinotecan and temozolomide with and without the addition of DFMO.

1.2.2 To define the toxicity profile of DFMO administered with dinutuximab, irinotecan and temozolomide.

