I/T/DIN therapy was generally well tolerated; however, several important toxicities were noted.^{4,5} Of the 51 patients evaluable for toxicity, 13 (25%) had \geq Grade 3 pain, 8 (16%) had \geq Grade 3 diarrhea, and 4 (8%) had \geq Grade 3 vomiting. Neutropenia (\geq Grade 3) was observed in 14 (27%), \geq Grade 3 thrombocytopenia in 5 (10%), and \geq Grade 3 fever/infection in 11 (22%). One patient experienced Grade 4 hypoxia and required mechanical ventilation for more than 24 hours. A second patient required discontinuation of dinutuximab therapy due to bronchospasm. One patient developed Grade 3 motor neuropathy which recovered 6 weeks following discontinuation of dinutuximab therapy. One patient died of sudden death 2 days following completion of the 14th cycle of dinutuximab based therapy and cause of death was undetermined despite all investigations including full autopsy. While the response rate to this regimen is quite promising, there remains room for improvement in terms of both response rate and regimen-associated toxicity.

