2.5 Dosing Rationale

In this trial, DFMO will be dosed orally. The bioavailability of orally administered DFMO ranges from 50-60% in multiple studies.²⁶ The dose of DFMO to be used for this trial (6,750 mg/m²/day divided 3 times a day orally) was the recommended phase 2 dose determined on the NANT consortium N2012-01 trial of DFMO in combination with cyclophosphamide, topotecan and celecoxib. The half-life of DFMO is 3-4 hours when delivered orally, therefore, a TID dosing regimen provides continuously higher plasma concentrations to optimize systemic polyamine depletion. DFMO will be given at this dose during therapy.

Starting with Amendment 2A, DFMO will be given on a discontinuous basis, allowing for a 7-day break without DFMO administration in each cycle, similar to the dosing used in the NANT N2012-01 trial. Four of the first eight patients enrolled on the DFMO containing arm (Regimen B) of this study with available ototoxicity data developed documented Grade 3 hearing loss from their baseline. Hearing loss is a known toxicity of DFMO and is typically reversible. Prior studies have shown that the risk of DFMO-associated ototoxicity is decreased when the DFMO is administered in an intermittent fashion, with a 7-14 day break per cycle. At similar or higher dosing compared to that used in ANBL1821, the incidence of Grade 3 or higher hearing loss with interrupted dosing was less than 5%^{40, 30, 29} Similarly, in the NANT2012-01 trial, DFMO dosed at 3000-9000 mg/m²/day for 21 days out of a 28-day cycle resulted in only 1 of 24 patients experiencing new Grade 3 hearing loss. This hearing loss was reversible and did not recur with re-treatment.³⁹ The NANT2012-01 trial was conducted in a relapsed NBL population similar to that of ANBL1821 supporting that intermittent dosing of

DFMO may decrease the risk for significant ototoxicity. Therefore, given the incidence of hearing loss seen initially on this study with continuous dosing, this trial will now include a 7-day break in DFMO dosing to decrease the chances of additional hearing loss. Additionally, DFMO will be held at first detection of significant hearing loss.

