DFMO PK data for lower DFMO doses in the NMTRC phase 1 study was linear between 1,000 and 3,000 mg/m²/day with mean C_{max} ranging from 40 µM to 120 µM.³⁸ On the NANT N2012-01 trial, mean C_{min} was measured at about 20 µM, 90 µM, 135 µM and 130 µM at dose levels of 3,000; 4,500; 6,750 and 9,000 mg/m²/day, respectively.³⁹ The estimated C_{max} (2-3 times C_{min} with these PK parameters) would therefore be > 270 µM at 6,750 mg/m²/day DFMO, the dose to be studied here. This is above the DFMO exposure threshold at which *in vitro* studies demonstrate effects on protein translation, and at which *in vivo* studies demonstrate anti-tumor activity and immunomodulatory effects on the TME.⁷

In this trial, DFMO will be combined with the backbone regimen of irinotecan and temozolomide with dinutuximab, which has been shown to be tolerable on the ANBL1221 study.³ The irinotecan/temozolomide regimen has fewer hematologic toxicities compared to cyclophosphamide/topotecan used in the previous NANT trial that combined DFMO with chemotherapy.^{3,41} This will likely decrease delays in treatment in a heavily pre-treated population. To limit unexpected or severe toxicities, this trial will closely monitor for increased toxicity on the DFMO arm compared to the standard arm consisting of dinutuximab, irinotecan, temozolomide and sargramostim, with specific attention to DFMO-related toxicities, including diarrhea and hearing loss. Starting with Amendment 4, patients will receive up to 6 cycles of protocol therapy due to changes in drug supply.

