4.5.5 Additional guidance

- Capillary leak syndrome is an expected side effect of dinutuximab therapy. Complications of capillary leak syndrome can be mitigated if euolemia is maintained. Close monitoring of heart rate and urine output is required, and fluids should be adjusted to compensate for third space losses. The routine use

of diuretics during Days 2-5 is contraindicated unless clinically required (i.e. pulmonary capillary leak with respiratory compromise). Use of furosemide should be avoided when feasible due to ototoxicity concerns.

- Corticosteroid therapy should be used only for life-threatening conditions (i.e. treatment of increased intracranial pressure in patients with CNS tumors, symptomatic bronchospasm, stridor unresponsive to other measures or life-threatening allergic reactions). Corticosteroids will impair the immune activation that is a critical part of the protocol therapy. **The use of steroids at any time during immunotherapy requires clear justification and documentation.**
- The use of IVIG is discouraged. IVIG should not be given within 2 weeks of starting dinutuximab treatment and 1 week after completing dinutuximab therapy.
- Cytokines or growth factors (G-CSF, Interferon, etc.) not included in the Treatment Plan are prohibited during immunotherapy.

4.6 **Regimen B Cycle 1**

4.6.1 Therapy Delivery Map –CYCLE 1 Cycle 1 lasts 4 weeks (28 days). This cycle includes a lead-in of 7 days of DFMO (Days -6 to 0) prior to 21 days of chemotherapy.	Patient COG ID number _____ DOB _____
---	--

Begin Cycle 2 on Day 22 of Cycle 1 or when peripheral counts recover with ANC \geq 750/ μ L and platelets \geq 75,000/ μ L (whichever occurs later). See [Section 5.0](#) for dose modifications. This TDM is on 3 pages.

DRUG	ROUTE	DOSAGE	DAYS	IMPORTANT NOTES
Eflornithine (DFMO) IND# 141913	PO or via NG or Gtube	2250 mg/m ² /dose x 3 doses/day See dosing table in Appendix XII	Days -6 to +7 and Days 15 - 21	Round doses to the nearest 500 mg (see dosing table in Appendix XII). Note: During Days 1-5, consider giving one of the 3 times daily eflornithine doses and temozolomide close together in order to minimize potential for emesis and redosing.

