9.3.4 Assessment of Study Objectives

The primary study aim ([1.1.1](#)) will be assessed by a one-sided continuity-corrected test of proportions with pooled variance to compare the response rates after 6 cycles in the two regimens, and the futility and efficacy monitoring rules ([Section 9.3.3](#)). The response rate by the end of 6 cycles will be calculated on each regimen, including placement of a 95% confidence interval. If a patient is a responder and later has PD or goes off protocol therapy, then the patient will be counted as a responder. If the response rate on Regimen B is significantly better, then it will be considered a therapeutic regimen worthy of further testing in patients with newly-diagnosed high-risk neuroblastoma. In addition, the response rate by the end of 6 cycles (based on confirmed responses) will also be calculated for each regimen, with responders defined as patients who achieve a confirmed minor response or better per the revised INRC⁶⁸ as their best overall response by the end of 6 cycles as determined by central review.

To address secondary objective [1.2.1](#), Kaplan-Meier curves of PFS and OS will be generated by regimen and compared using log-rank tests. PFS and OS will also be evaluated separately in the cohorts of patients enrolled prior to and post-Amendment 4 given the reduction in maximum cycles of therapy from 17 to 6 cycles.

To assess secondary aim [1.2.2](#), toxicities (Grade ≥ 3) experienced on Regimen B will be descriptively summarized.

Exploratory aim [1.3.1](#) will be assessed by exploring the relationship between response (responder vs. non-responder) after 6 cycles on Regimen B with serum cytokine levels (IL1, IL6, TNF-alpha, IFN-gamma, etc.), tumor resident immune cells (NK cells, TAMS, TILS), and critical immune cell suppressing proteins (B7H3, PDL-1) using Fisher's exact test for categorical and Wilcoxon rank-sum test for continuous factors.

To address exploratory objective [1.3.2](#), GD2 levels in tumor cells from bone marrow samples will be correlated with response (responder vs. non-responder) after 6 cycles using Fisher's exact test for categorical and the Wilcoxon rank-sum test for continuous factors.

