To assess exploratory aim [1.3.3](#), the occurrence of pain on each regimen as reported by patient report and opiate use will be descriptively summarized. Descriptive and summary statistics will be used to describe the scores from the Faces Pain Scale-Revised during the dinutuximab infusion and on Day 1 with irinotecan and temozolomide alone for each arm separately. Confidence intervals will be constructed for the mean and frequency estimates. The Day 1 patient reported outcome data are expected to be similar between the 2 regimens, while differences during or after completion of treatment may be observed.

9.4 **Evaluability for Response**

All eligible patients will be considered evaluable for response.

9.5 **Evaluability for Toxicity**

All eligible patients will be evaluable for toxicity from the time of their first treatment with eflornithine, irinotecan, temozolomide, or dinutuximab.

The study committee will review ototoxicity data closely during monthly committee meetings. If a difference in the incidence of hearing loss of $>15\%$ in eligible patients treated on the interrupted schedule enacted with Amendment 2A is detected among patients on the DFMO-containing Regimen B as compared to Regimen A, the study committee will notify the DSMC and CTEP and discuss potentially suspending accrual and further modifying the DFMO dose and/or schedule. In this context, hearing loss is defined as “an increase of 15dB or more from baseline in hearing threshold at two contiguous frequencies between 500-3000Hz” as this is the criterion for which DFMO is held for hearing loss.

9.6 **Gender and Minority Accrual Estimates**

The gender and minority distribution of the study population is expected to be:

DOMESTIC PLANNED ENROLLMENT REPORT								
Racial Categories	Ethnic Categories						Total	
	Not Hispanic or Latino		Hispanic or Latino					
	Female	Male	Female	Male				

American Indian/ Alaska Native	0	0	0	0	0
Asian	0	3	0	0	3
Native Hawaiian or Other Pacific Islander	0	0	0	0	0
Black or African American	8	5	0	0	13
White	18	29	5	10	62
More Than One Race	0	0	0	0	0
Total	26	37	5	10	78

INTERNATIONAL (including Canadian participants) PLANNED ENROLLMENT REPORT						
Racial Categories	Ethnic Categories				Total	
	Not Hispanic or Latino		Hispanic or Latino			
	Female	Male	Female	Male		
American Indian/ Alaska Native	0	0	0	0	0	
Asian	0	2	0	0	2	
Native Hawaiian or Other Pacific Islander	1	1	0	0	2	
Black or African American	0	0	0	0	0	
White	4	7	2	0	13	

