11.12 Routine Adverse Event Reporting

Note: The guidelines below are for routine reporting of study specific adverse events on the COG case report forms and do not affect the requirements for CTEP-AERS reporting.

Routine reporting is accomplished via the Adverse Event (AE) Case Report Form (CRF) within the study database. For this study, routine reporting will include all toxicities reported via CTEP-AERS and all Grade 3 and higher Adverse Events.

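### Section 9.3.4 summarises Grade 3 or higher toxicity for secondary aim 1.2.2 on Regimen B only; a by-regimen table with risk differences would show what DFMO adds, using data already collected

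*Combined protocol and SAP*

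**What the plan says.** Section 1.2 words aim 1.2.2 as "To define the toxicity profile of DFMO administered with dinutuximab, irinotecan and temozolomide". The only analysis given for it, in Section 9.3.4, is that Grade 3 or higher toxicities "experienced on Regimen B will be descriptively summarized". No Regimen A column, difference or interval is mentioned.

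Other parts of the plan look at both arms:

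- Section 2.5 states that "this trial will closely monitor for increased toxicity on the DFMO arm compared to the standard arm", naming diarrhea and hearing loss.
- For exploratory aim 1.3.3, Section 9.3.4 says that "the occurrence of pain on each regimen as reported by patient report and opiate use will be descriptively summarized", with confidence intervals.
- Section 9.5 makes all eligible treated patients evaluable for toxicity. It also sets a hearing-loss difference of more than 15% between regimens, on the interrupted schedule, as the point at which the study committee notifies the DSMC and CTEP.
- Section 11.12, with no restriction by arm, says that "routine reporting will include all toxicities reported via CTEP-AERS and all Grade 3 and higher Adverse Events".

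Three further provisions affect how a comparison would be built. Section 3.2.6.1 makes patients with known marrow involvement not evaluable for hematological toxicity. Section 4.6.1 says of Regimen B Cycle 1: "This cycle includes a lead-in of 7 days of DFMO (Days -6 to 0) prior to 21 days of chemotherapy". Audiograms fall after Cycles 2 and 6 on Regimen A (Section 4.5.2) but after every second cycle on Regimen B (Section 4.7.2).

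**The concern.** All the backbone drugs continue on Regimen B, so its event rate is the sum of backbone toxicity and whatever DFMO contributes. In ANBL1221 the backbone's own toxicity was not small: "Of the 51 patients evaluable for toxicity, 13 (25%) had" Grade 3 or higher pain, and 8 of 51 had diarrhea of that grade. Historical rates from 51 patients are too imprecise to subtract. The 1:1 randomised control removes the problem at no cost in data, yet the analysis text leaves it out for a secondary safety aim while using it for an exploratory pain aim.

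The protocol abstract says a successful regimen would move into frontline induction. Anyone planning that step would want to know how much toxicity DFMO adds. The question has already come up within the trial: "Four of the first eight patients enrolled on the DFMO containing arm (Regimen B) of this study" with available ototoxicity data had Grade 3 hearing loss, and the DFMO schedule was changed at Amendment 2A (Section 2.5).

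On hearing, the Section 9.5 comparison is between arms tested at different frequencies. More tests give more chances to record a transient loss or a noisy reading.

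**Working it through.** **1. The plan's own size.** Section 9.3.1.1 gives 45 per regimen for 40% versus 60%, one-sided 20%, power 80%, with continuity correction.
- Uncorrected: n = [0.8416·√(2·0.5·0.5) + 0.8416·√(0.24 + 0.24)]² / 0.20² = 34.7.
- Corrected: (34.7/4)·[1 + √(1 + 4/(34.7·0.20))]² = 44.1, so 45. This matches.
- The documents state no size or power for toxicity.

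**2. What historical control can support.** Exact 95% intervals for the ANBL1221 rates (Section 2.1):
- diarrhea 8/51 = 15.7% (7.0 to 28.6)
- pain 13/51 = 25.5% (14.3 to 39.6)

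**3. Illustration, counts assumed.** Take Grade 3 or higher diarrhea in 14/45 on Regimen B. The planned summary gives 31.1% (exact 95% CI 18.2 to 46.6). Risk difference B − A with Newcombe 95% intervals:

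| Regimen A (assumed) | A rate | B − A, points | 95% CI |
|---|---|---|---|
| 4/45 | 8.9% | +22.2 | 5.7 to 37.7 |
| 7/45 | 15.6% | +15.6 | −2.0 to 32.1 |
| 11/45 | 24.4% | +6.7 | −11.7 to 24.4 |

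All three A rates lie inside the ANBL1221 interval. The same Regimen B summary is therefore compatible with quite different added toxicity.

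**4. Precision of the comparison.** Approximate 95% half-width with equal rates: 1.96·√(2p(1−p)/n).
- 45 per arm: diarrhea (p = 8/51) 15.0 points; pain (13/51) 18.0.
- 74 per arm (the optional larger size): 11.7 and 14.0.
- Hematologic events are less precise after the Section 3.2.6.1 exclusion. For neutropenia (14/51 in ANBL1221) the half-width is 18.4 points with all 45 per arm and 22.6 if, as an assumption, 30 per arm remain.

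**5. Observation windows.** Six cycles of 21 days are 126 planned days on Regimen A. With the 7-day lead-in, Regimen B has 133.

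**6. Hearing.** The documents give no per-test rate. Assume independent tests with the same probability p of recording a loss in both arms. The expected spurious gap is (1−p)^kA − (1−p)^kB.
- Through Cycle 6, B has 3 tests and A has 2, so the gap is p(1−p)². At p = 3%, 5%, 10% it is 2.8, 4.5, 8.1 points. Its maximum over all p is 4/27 = 14.8 points, at p = 1/3.
- With an end-of-therapy test in both arms (4 versus 3), the gap is p(1−p)³: 2.7, 4.3, 7.3 points, maximum 27/256 = 10.5.
- These bounds are for patients tested through the end of Cycle 6. A monthly review also includes patients between the Cycle 4 and Cycle 6 tests, with 2 tests against 1. Their gap is p(1−p): 2.9, 4.8, 9.0 points at the same rates, reaching 15 only when p exceeds about 18%.
- At 17 cycles, open only to patients enrolled before Amendment 4 who keep a minor response or better, the count is 8 versus 2 and the gap is 15.7, 23.9, 38.0 points.

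**The case against.** The strongest reply is that the analysis matches the aim. Aim 1.2.1 says compare; aim 1.2.2 says define a profile. Section 9.3.4 follows that distinction, with log-rank tests for one and a description for the other. That stands: the plan does not contradict itself.

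A reader might infer that toxicity is never compared between arms. The documents do not support that. Section 2.5 states an intent to monitor against the standard arm, Section 9.5 compares hearing, pain is summarised on each regimen, and the DSMC receives interim toxicity reports (Section 12.2). What lacks Regimen A is the analysis stated for aim 1.2.2.

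Nor do the documents tie further testing to a toxicity difference. Section 9.3.4 makes that conclusion depend on response rate. The added-toxicity estimate is useful to that decision, but it is not a condition of it.

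A comparison at 45 per arm is imprecise. That also stands, and is why estimates with intervals are proposed and no test.

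On hearing, a reader might infer that unequal testing alone could trip the 15% trigger. For patients tested through Cycle 6 under the current maximum, the expected gap stays below 15 points at every per-test rate in this model. The 17-cycle figures apply only to a subset of patients enrolled before Amendment 4, whose share is not given. They also rest on assumed, independent per-test rates that nothing in the documents supports. If losses persist once they occur, the inflation is small. Crossing the trigger leads to notification and discussion, not an automatic stop.

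**Conclusion.** The concern holds as an improvement to the stated analysis, not as an error against the aim. A Regimen B-only summary cannot separate DFMO's contribution from the backbone's, and the data to do so are already in hand. The gain is an unconfounded estimate of added toxicity, with half-widths of about 15 to 18 points for diarrhea and pain at 45 per arm and wider for hematologic events once marrow-involved patients are excluded. The worked counts are assumptions; the ANBL1221 rates and the sample size are the protocol's.

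The hearing point is secondary and modest: about 3 to 8 points through Cycle 6 at assumed per-test rates of 3% to 10%, and only if losses are transient or test noise. At those assumed rates, a gap that reaches 15 points needs patients enrolled before Amendment 4 and treated well beyond Cycle 6.

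**What to change.** In Section 9.3.4, replace the sentence for aim 1.2.2 with one to this effect:

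> Grade 3 or higher toxicities will be tabulated by regimen, with risk differences and 95% confidence intervals, from first study treatment through Cycle 6. Hematologic toxicities will exclude patients with marrow involvement (Section 3.2.6.1).

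Table notes should then:

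- show Regimen B lead-in events (Days -6 to 0) on their own line;
- show cycles after Cycle 6 separately (patients enrolled before Amendment 4 only);
- show results by the DFMO schedule actually received, continuous or interrupted, each beside concurrent Regimen A patients, with a stated rule for anyone who changed schedule at Amendment 2A. Section 9.5 also goes by schedule received, and enrollment date could misplace such patients. Give counts only where a group is too small for useful intervals.

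In Section 9.5, keep the trigger as written. Report beside it the between-arm difference at the shared audiogram time points (end of Cycle 2, end of Cycle 6, end of therapy, 12 months), with the number tested per arm. That difference depends on who is still being tested, so it accompanies the trigger figure and does not replace it.

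The cost is a short text change in two sections and some extra tabulation. No new tests or data are needed, and sample size, error rates, the trigger threshold and patient management do not change.

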1.3 Exploratory Aims

1.3.1 To characterize the immune and cytokine profiles of patients treated with DFMO/chemotherapy/dinutuximab combination and correlate with response to therapy.

1.3.2 To evaluate GD2 levels in tumor cells from patient bone marrow samples and correlate with response to therapy.

1.3.3 To explore whether the addition of DFMO to the dinutuximab and chemotherapy backbone affects pain as determined by patient report and opiate usage.

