Preliminary studies evaluating rat models of allodynia demonstrate that DFMO may reduce dinutuximab induced pain sensation (personal communication, [name]). Furthermore, pro-inflammatory cytokines have been linked to neuropathic pain and the immunomodulatory effects of DFMO may influence such cytokine levels.⁵⁶ Therefore, the association between inflammatory serum cytokine levels (IL1, IL6, TNF-alpha, IFN-gamma, etc.), pain, and DFMO therapy merit evaluation. This exploratory aim is to examine the change in pain during dinutuximab infusion in the patients on the DFMO arm compared to the control arm as determined by the Faces Pain Scale. Patients over the age of 5, and proxy for those under the age of 5, will complete the Faces Pain Scale-Revised on Day 1 of chemotherapy with irinotecan and temozolomide, and then daily during the dinutuximab infusion. This will be measured during Cycles 1, 2, 4, and 6. Patients enrolled prior to Amendment 4 will also have the Faces Pain Scale-Revised collected during Cycle 12 of therapy. The Faces Pain Scale-Revised is a simple visual scale validated to provide real-time pain assessment in the pediatric and adolescent and young adult (AYA) population.⁵⁷ It has been recommended as the superior PRO measure for pain in pediatric populations based on its excellent psychometric properties and responsiveness to change.⁵⁸ The scale scores pain based on a visual cue on a scale of 0 to 10. Pain will also be assessed by measuring the amount of intravenous narcotic administered during the dinutuximab infusion. Patients will also be evaluated for differences in pro-inflammatory cytokine levels during dinutuximab infusion.

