14.1.3.1 Timing

Administer the Faces Pain Scale Revised at any time on Day -6 (Cycle 1 of Regimen B only) and Day 1 of therapy with irinotecan and temozolomide alone, and then on Days 2-5 of therapy at least 4 hours after the dinutuximab infusion has begun. It will be administered during Cycles 1, 2, 4, 6 for all patients and Cycle 12 of therapy for patients enrolled prior to Amendment 4.

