14.1.3.2 Assessments

The assessments will be performed by the nurse caring for the patient at the appropriate time-points described above. The data will be entered in RAVE. The total daily intravenous narcotic dose will also be entered in RAVE.

14.2 **Optional Studies**

The following correlative studies are optional, but **strongly encouraged**. All patients will be eligible for all special studies on ANBL1821.

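### Exploratory aim 1.3.3 asks whether pain differs between the arms, but Section 9.3.4 plans no between-arm estimate and describes Day 1 in a way that does not fit Regimen B

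*Combined protocol and SAP*

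**What the plan says.** Section 1.3 words aim 1.3.3 as a question about an effect of treatment: "To explore whether the addition of DFMO to the dinutuximab and chemotherapy backbone affects pain as determined by patient report and opiate usage". Section 2.6.3 makes the comparison explicit; the purpose is to "examine the change in pain during dinutuximab infusion in the patients on the DFMO arm compared to the control arm".

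Section 9.3.4 answers with summaries by arm. It says that "the occurrence of pain on each regimen as reported by patient report and opiate use will be descriptively summarized", and that Faces Pain Scale-Revised (FPS-R) scores will be described during the infusion and "on Day 1 with irinotecan and temozolomide alone for each arm separately". Intervals are promised for means and frequencies. The paragraph ends with the expectation that "The Day 1 patient reported outcome data are expected to be similar between the 2 regimens", and adds that differences may be seen later. It names no between-arm difference, test or model. By contrast, the same section names Fisher's exact and Wilcoxon rank-sum tests for aims 1.3.1 and 1.3.2.

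Section 14.1.3.1 schedules the scale on Day 1 and Days 2-5 of Cycles 1, 2, 4 and 6 (also Cycle 12 for patients enrolled before Amendment 4). It adds a Day -6 score in Cycle 1 of Regimen B only. Section 9.3.4 gives the Day -6 score no role. On opioids, Section 14.1.3.2 states: "The total daily intravenous narcotic dose will also be entered in RAVE".

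**The concern.** Two things look wrong.

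First, the question is comparative and the arms are randomised, but the planned output stops at one interval per arm. A reader who wants the DFMO effect must derive it from two separate summaries, with no planned interval for it.

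Second, Section 9.3.4 presents Day 1 as a point where the arms should agree. In Regimen B that score is taken after DFMO has started. Section 2.6.3 itself argues that DFMO may reduce allodynia and alter pain-related cytokines. If the change in pain mentioned in Section 2.6.3 were measured from Day 1, a DFMO effect already present on Day 1 would be lost from the comparison.

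Opioid use raises a related question. Opioids are titrated to pain, so similar scores can go with different opioid need. The opioid measure therefore has to be interpretable across the three drugs that the protocol allows.

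**Working it through.** **Patients available.** The documents give no sample size for the pain aim, so the primary design fixes it. Section 9.3.1.1 states 45 per arm for 40% versus 60%, one-sided alpha 0.20, 80% power, continuity-corrected.
- Uncorrected n = [0.8416 × √(2 × 0.5 × 0.5) + 0.8416 × √(0.24 + 0.24)]² / 0.20² = 34.7.
- Corrected n = (34.7 / 4) × [1 + √(1 + 4 / (34.7 × 0.20))]² = 44.1, rounded up to 45.

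The stated 45 per arm is reproduced, with power of 80.6%.

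**Is a between-arm interval feasible?** The FPS-R runs from 0 to 10. Its standard deviation is not in the documents, so 2 to 3.5 is assumed. With one score per patient, the half-width for the difference is 1.96 × SD × √(2/45) = 0.413 × SD.
- SD 2: 0.83 points
- SD 2.5: 1.03
- SD 3: 1.24
- SD 3.5: 1.45

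**Do separate intervals substitute for it?** With equal standard errors SE, two 95% intervals fail to overlap when the difference exceeds 2 × 1.96 × SE. The standard error of the difference is √2 × SE, so this needs z above 3.92 / √2 = 2.77, a two-sided level of about 0.006. Judging by overlap is much stricter than using a 95% interval for the difference.

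**What Day 1 is.**
- Section 4.1: Regimen B has DFMO on Days -6 to 0, which is seven days before Day 1 of Cycle 1.
- Section 4.6.3: DFMO in Cycle 1 runs through Day 7, so it is also given on Day 1.
- Sections 4.6.3 and 4.7.3: DFMO is also scheduled on Days 15-21, so Day 1 of Cycles 2, 4 and 6 follows DFMO, as well as earlier dinutuximab.
- Section 4.4.2: in Regimen A the Day 1 score may be taken at any time that day, so it can follow chemotherapy.

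If DFMO lowers the Day 1 score by d, a change-from-Day-1 comparison understates its effect during the infusion by d. Pairing Day -6 in Regimen B with Day 1 in Regimen A does not solve this, because the two scores are taken under different conditions.

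**Opioid scale.** These are the starting doses in Section 4.6.4 (the same in the other regimen sections), used here only to show the scale of the numbers. Totals are loading dose plus 10 hours of continuous infusion.
- Morphine: 0.1 + 10 × 0.02 = 0.300 mg/kg
- Hydromorphone: 0.02 + 10 × 0.004 = 0.060 mg/kg
- Fentanyl: 0.001 + 10 × 0.0005 = 0.006 mg/kg

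Morphine is 5 times the hydromorphone figure and 50 times the fentanyl figure. At 20 hours the fentanyl ratio is 0.500 / 0.011, about 45. The morphine-to-fentanyl ratio is not unique: 100:1 for the loading dose, 40:1 for the infusion (0.02 mg versus 0.5 mcg) and 40:1 for as-needed doses (0.01 mg versus 0.25 mcg).

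Illustration with assumed drug mixes and equal need, if milligrams were pooled:
- Morphine/fentanyl 80/20 in A: 0.8 × 0.300 + 0.2 × 0.006 = 0.241 mg/kg
- Morphine/fentanyl 60/40 in B: 0.6 × 0.300 + 0.4 × 0.006 = 0.182 mg/kg

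This is a spurious 24% reduction. With 90/10 versus 80/20 it is 11%.

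**The case against.** The aim is exploratory, and a descriptive analysis is a legitimate choice for it. Each arm is summarised with intervals, so the point difference can be derived by subtraction. That stands, and it limits the severity. A reader might infer that the trial cannot answer aim 1.3.3 at all. The documents do not support that: the data are collected in both randomised arms, and only the contrast and its interval are missing from the plan.

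A reader might also infer that the plan subtracts Day 1. Section 9.3.4 defines no change-from-Day-1 endpoint. It states an expectation and summarises Day 1 by arm, so the expectation can be checked. Since dinutuximab starts on Day 2, similar Cycle 1 Day 1 scores are not an unreasonable guess, and the word alone may simply mean without dinutuximab. What remains is that the label omits DFMO in Regimen B, and that Section 2.6.3 speaks of change without naming a baseline.

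On repeated scores, a reader might infer that the intervals will be far too narrow. With 16 infusion-day scores (4 days × 4 cycles) treated as independent and an assumed within-patient correlation of 0.3 to 0.6, the design effect is 1 + 15 × 0.3 = 5.5 to 1 + 15 × 0.6 = 10. Intervals would then be too narrow by a factor of 2.3 to 3.2. The plan does not say that scores are pooled; day-by-day summaries would have a design effect of 1. Many patients will also have fewer than 16 scores, because therapy stops for progression or toxicity (Section 8.1).

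On opioids, pooling of raw milligrams is likewise not stated. The case report form is not in the documents and may hold the drug name. Morphine is described as the most commonly used drug, and randomisation balances drug choice in expectation, so a mixed scale would mainly add noise.

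**Conclusion.** The concern holds as a minor point. The aim is comparative, and Section 9.3.4 plans neither a between-regimen difference nor an interval for it. That rests on the text alone. The description of Day 1 does not fit Regimen B, where the Cycle 1 score follows seven days of DFMO. The resulting bias is conditional: it arises only if Day 1 is used as a reference, and its size equals whatever DFMO has already done to the Day 1 score, which is unknown. For opioid use, the finding is that no common scale or weight adjustment is stated.

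The 100-fold difference between opioids is true of the loading dose only. Over a day of 10 to 20 hours' infusion at starting doses it is about 45- to 50-fold, and it matters only if milligrams are combined across drugs.

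The precision figures assume 45 scored patients per arm and a standard deviation of 2 to 3.5. No primary or secondary conclusion is affected.

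**What to change.** Amend the aim 1.3.3 paragraph of Section 9.3.4 before analysis:

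- **Contrast.** Estimate the Regimen B minus Regimen A difference in infusion-day FPS-R scores with a 95% confidence interval. Make Cycle 1 Days 2-5 the main contrast, before much attrition. Use either one summary score per patient, or a mixed model with a patient random effect and terms for day, cycle and age group/proxy report.
- **Day 1.** Correct its label for Regimen B. Do not use it as a baseline or covariate. Report it by regimen as a post-DFMO outcome, and describe Day -6 in Regimen B only, as it has no counterpart in Regimen A.
- **Opioids.** Report the between-regimen difference in daily intravenous opioid use per kg on a common scale, using one conversion table fixed before analysis. The protocol's starting doses cannot serve as that table, because their ratios are not unique. Alternatively, stratify by drug.

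The cost is some extra analysis, with no new patients or visits. The opioid name must be kept with each dose if the case report form does not already hold it.
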